### 1.3.2. Schedule of Activities – Long-term Extension Treatment Period

Period	Long-term Extension Treatment Period										Safety follow-up a	Early Termination b	Notes
Week	64	76	88	100	112	124	136	148	156	160 or 4 weeks after the last dose			
Visit Windows (Days)	±6	±6	±6	±6	±6	±6	±6	±6	±6	±6	±6		
Study Procedures													
Study Intervention Administration													
Dispense study intervention c	X	X	X	X	X	X	X	X					
Administer study intervention	Oral study intervention will be self-administered daily (Section 6.1).												
Study intervention accountability	X	X	X	X	X	X	X	X	X				
Efficacy Assessments													
PROs: Complete in the order shown before any tests, procedures, or consultations for all visits unless otherwise noted.													
DLQI (only for participants ≥18 years of age on the first date of Screening)	X	X	X	X	X	X	X	X	X		X		
CDLQI (only for participants ≥12 to <18 years of age on the first date of Screening)	X	X	X	X	X	X	X	X	X		X		
EQ-5D-5L	X			X			X		X			X	
Clinician-reported Outcomes (ClinROs)													
CGI d	X	X	X	X	X	X	X	X	X		X		
JDA severity index for participants with GPP e	X	X	X	X	X	X	X	X	X		X		
BSA for participants with EP	X	X	X	X	X	X	X	X	X		X		
PASI	X	X	X	X	X	X	X	X	X		X		
IGA	X	X	X	X	X	X	X	X	X		X		
Safety Assessments													
Full physical examination					X				X		X		
Targeted physical examination f	X	X	X	X		X	X	X		X			
Height g					X				X				
Weight					X				X		X		
Vital signs h	X	X	X	X	X	X	X	X	X	X	X		
12-lead ECG					X				X		X		
PHQ-9 i	X	X	X	X	X	X	X	X	X	X	X		
C-SSRS i	X	X	X	X	X	X	X	X	X	X	X		

Period	Long-term Extension Treatment Period										Safety follow-up a	Early Termination b	Notes	
Week	64	76	88	100	112	124	136	148	156	160 or 4 weeks after the last dose				
Visit Windows (Days)	±6	±6	±6	±6	±6	±6	±6	±6	±6	±6	±6			
TB evaluation j	X	X	X	X	X	X	X	X	X	X	X	X		
Pregnancy test for female participants of childbearing potential k	X	X	X	X	X	X	X	X	X	X	X	X		
Clinical Laboratory Tests														
Hematology	X		X		X		X		X	X @	X	@only required if clinically significant at the previous visit.		
Chemistry	X		X		X		X		X	X @	X			
Urinalysis l	X		X		X		X		X		X			
Clinical Pharmacology Assessments														
JNJ-77242113 concentration (plasma) m	X				X				X		X			

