### **7. DISCONTINUATION OF STUDY INTERVENTION AND PARTICIPANT DISCONTINUATION/WITHDRAWAL**

#### **7.1. Discontinuation of Study Intervention**

If a participant discontinues study intervention for any reason before the end of the study, then the ET Visit assessments must be obtained (Section 1.3) as soon as possible. Study intervention assigned to the participant who discontinued study intervention may not be assigned to another participant (Section 6.2). Additional participants will not be entered in this study. Participants who discontinue study intervention but do not terminate study participation will continue to return for protocol specified procedures and evaluations. Discontinuation from study intervention does not mean that the participant is required to withdraw informed consent and leave the study.

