#### **8.4.1. Time Period and Frequency for Collecting Adverse Event and Serious Adverse Event Information**

##### **All Adverse Events**

All AEs and special reporting situations, whether serious or non-serious, will be reported from the time a signed and dated ICF is obtained until completion of the participant's last study-related procedure, which may include contact for follow-up of safety. All AEs with an onset date after the signing of the ICF and up to 4 weeks after study intervention discontinuation must be recorded on specific AE pages of the eCRF.

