#### **8.4.5. Adverse Events of Special Interest**

An AESI, which may be serious or non-serious, is an AE of scientific and medical concern specific to the sponsor's product or program, for which ongoing monitoring and expedited communication (within 24 hours) by the investigator to the sponsor is warranted. The AESIs for JNJ-77242113 are active TB, malignancy, and possible Hy's Law cases.

A **possible Hy's Law case** is defined by the occurrence of ALT/AST  $\geq 3$  x ULN together with Tbili  $\geq 2$  x ULN or INR  $> 1.5$  (if measured). Any possible Hy's Law case is considered an important medical event and must be reported to the sponsor in an expedited manner using the AESI form, even before all other possible causes of liver injury have been excluded ([FDA 2009](#)). AESI must be reported using the SAE form.

Any newly identified malignancy or case of active TB occurring after the first administration of study intervention must be reported by the investigator according to the procedures in [Appendix 3: Adverse Events, Serious Adverse Events, Product Quality Complaints, and Other Safety Reporting: Definitions and Procedures for Recording, Evaluating, Follow-up, and Reporting](#). Investigators are also advised that active TB is considered a reportable disease in most countries/territories.

An AESI is considered serious only if it meets the definition of an SAE.

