4.5.2. Adverse Events

The verbatim terms used in the CRF by investigators to identify adverse events will be coded using MedDRA. In general, any AE occurring at or after the initial administration of study intervention up to 4 weeks after the last dose or treatment discontinuation is considered to be treatment emergent. If the event occurs on the day of the initial administration of study intervention, and either event time or time of administration are missing, then the event will be assumed to be treatment emergent. If the event date is recorded as partial or completely missing, then the event will be considered to be treatment emergent unless it is known to be prior to the first administration of study intervention based on partial onset date or resolution date. All reported treatment-emergent adverse events will be included in the analysis. For each adverse event, the number and percentage of participants who experience at least 1 occurrence of the given event will be summarized.

Summary tables will be provided for treatment-emergent adverse events:

- AEs
- AEs with frequency of at least 2 participants in ‘GPP+EP’ column
- SAEs
- AEs leading to discontinuation of study intervention
- AEs by severity
- AEs by relationship to study intervention
- SAEs by relationship to study intervention
- AEs by study period

In addition to the summary tables, listings will be provided for treatment-emergent adverse events:

- AEs
- SAEs
- AEs leading to death
- AEs leading to discontinuation of study intervention
- AEs for psoriasis
- Suicidal ideation or suicidal behavior
- Had hypersensitivity including anaphylactic reactions

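### SAP 4.5.2 ends the treatment-emergent period at 4 weeks without declaring the change from Protocol 9.3.5, and AEs and SAEs with later onset in participants still being followed have no clear recording rule and no planned output

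*SAP*

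**What the plan says.** **Analysis window.** SAP 4.5.2 treats an AE from first administration "up to 4 weeks after the last dose or treatment discontinuation is considered to be treatment emergent". The outputs follow that definition: "Summary tables will be provided for treatment-emergent adverse events", and "In addition to the summary tables, listings will be provided for treatment-emergent adverse events". The listings include those for all AEs, SAEs and AEs leading to death. Protocol 9.3.5 (Adverse Events) defines treatment-emergent from first administration with no closing date. The SAP version history presents the 4-week wording as a clarification, and SAP 4.8, the table of departures from the protocol, omits it.

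**Recording window.** Protocol 8.4.1 first says that all AEs, "whether serious or non-serious, will be reported from the time a signed and dated ICF is obtained until completion of the" participant's last study-related procedure. It then says: "All AEs with an onset date after the signing of the ICF and up to 4 weeks after study intervention discontinuation must be recorded" on the AE pages of the eCRF. The SAE paragraphs have the same split. All SAEs during the study go to the sponsor, but recording on the eCRF and SAE form is required only to 4 weeks after discontinuation. Section 8.3 and SoA notes t (to Week 52) and n (extension) require AE recording with no 4-week limit.

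**Who is followed past 4 weeks.** Protocol 7.1 says: "Participants who discontinue study intervention but do not terminate study participation will continue to return for protocol specified procedures and evaluations". The early-termination footnote to SoA 1.3.2 describes only a termination visit and a return about 4 weeks after the last dose. That safety follow-up visit is scheduled at Week "160 or 4 weeks after the last dose", with a window of ±6 days.

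**The concern.** The safety endpoint is the frequency and type of AEs and SAEs, with no treatment-emergent limit in its wording. Under Protocol 9.3.5, an SAE that begins three months after the last dose in a participant still attending visits would be counted. Under SAP 4.5.2 it enters no table and no listing in that section. Whether it reaches the eCRF at all depends on which sentence of 8.4.1 the site follows.

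The participants affected are those who stopped study drug early. The mandatory stopping reasons in Protocol 7.1.3 include malignancy, opportunistic or recurrent serious infection, active TB and liver abnormality, so later events in this group deserve to be visible. The study has 16 participants, no control arm and no Data Monitoring Committee, which makes each event influential. A reader of the SAP would not learn from 4.8 that the definition had been narrowed.

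**Working it through.** **1. The plan's own timing.** Protocol 4.1 gives about 165 weeks per participant: 5 + 52 + 104 + 4 = 165. The extension ends at Week 156, and 156 + 4 = Week 160, which matches the SoA. The timetable is consistent for participants who complete treatment.

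**2. Safety follow-up visit.** 4 weeks = 28 days, and the window is ±6 days, so the visit falls on days 22 to 34 after the last dose. At most 34 − 28 = 6 days lie beyond the limit, and only when the visit is late.

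**3. Participants who stop drug but stay on visits.** The window closes at (week of last dose + 4), and time outside it to Week 52 is 52 − (week of last dose + 4). The remaining visits come from the SoA (Weeks 2, 4, 8, 12, 16, 20, 24, 28, 32, 36, 44, 52), counting a visit in the closing week as inside. AE review is marked at each. The weeks of last dose are illustrative, because the documents give no discontinuation rate.

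| Last dose (week) | Window closes (week) | Weeks outside, to Week 52 | Visits with AE review outside |
|---|---|---|---|
| 4 | 8 | 44 | 9 |
| 16 | 20 | 32 | 6 |
| 24 | 28 | 24 | 4 |
| 36 | 40 | 12 | 2 |

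**4. Weight of one event (Clopper-Pearson 95% CI).**

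| Group | No event | One event |
|---|---|---|
| One disease group (n = 8) | 0/8 = 0% (0 to 36.9%) | 1/8 = 12.5% (0.3 to 52.7%) |
| Both groups (n = 16) | 0/16 = 0% (0 to 20.6%) | 1/16 = 6.25% (0.2 to 30.2%) |

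This is what any single event is worth at this sample size. It does not estimate how many would be missed.

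**5. Where a late event could appear.**

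| Event with onset after 4 weeks, participant still in study | eCRF recording | Planned AE, SAE, AESI or death output |
|---|---|---|
| AE, not an AESI | Required by 8.3 and notes t and n; not required by the second sentence of 8.4.1 | None |
| SAE, not an AESI and not fatal | Sponsor report required; eCRF rule as above | None |
| AESI | Reporting required by 8.4.5 | AESI listing (SAP 4.5.2.1), no stated limit |
| Death | eCRF rule for a fatal SAE as above | Death listing (SAP Appendix 1), no stated limit |

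The first two rows are the gap. Protocol 10.3.1 refers back to 8.4.1 for the end of AE recording, so 8.4.1 is the place to settle it.

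**6. Is 4 weeks short for this drug?** Protocol 2.2 gives a half-life of about 9 to 12 hours. 28 × 24 = 672 hours; 672/12 = 56 and 672/9 ≈ 75 half-lives.

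**The case against.** The strongest reply is that a 4-week window is a sound analysis choice. It spans some 56 to 75 half-lives, and inclusion criterion 8 places the end of relevant systemic exposure at 4 weeks after the last dose. Adding months off drug, perhaps on other therapy, would blur attribution. This stands, and it is why the window should remain for the tables. It does not explain why the narrowing is undeclared or why later events have no listing.

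It can also be said that the 4-week sentence in 8.4.1 sets a minimum and bars nothing, and that Section 8.3 and notes t and n already ask for later events. This stands too. The defect is an inconsistency that may lead sites to record differently, and no loss of data has been shown.

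The number affected is unknown. Section 7.1 covers only those who remain in the study, and the SoA footnote may be read as ending their visits at about 4 weeks.

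A reader might go further in three ways that the documents do not support:

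- **That events found at a late visit drop out.** The cut-off acts on onset. An event found on day 34 with onset by day 28 counts, and under SAP 4.5.2 missing or partial dates default to treatment-emergent unless onset is known to precede first dose.
- **That the window should run to day 34.** The 6-day difference is trivial for this half-life, and tying the window to the visit date would give participants windows of different length for scheduling reasons.
- **That 8.4.5 contradicts 8.4.1.** Section 8.4.5 says: "Any newly identified malignancy or case of active TB occurring after the first administration of study intervention must be reported by the investigator". That adds a duty for two event types and does not conflict with the general rule.

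**Conclusion.** The concern holds in a limited form. SAP 4.5.2 narrows the protocol's treatment-emergent definition without listing this in 4.8. Protocol 8.4.1 is inconsistent with itself, with Section 8.3 and with SoA notes t and n on how long AEs and SAEs go on the eCRF. Together these leave AEs and SAEs with onset more than 4 weeks after the last dose, other than AESIs and deaths, with uncertain recording and no planned AE or SAE output.

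The size depends on how many participants stop early and stay, which the documents do not give. If one stays to Week 52, 12 to 44 weeks and 2 to 9 scheduled AE reviews lie outside the window for last doses between Week 36 and Week 4. This assumes that Section 7.1, and not the SoA footnote, describes what happens. The matter is one of transparency and completeness. It does not invalidate the planned AE tables, and the correction is cheap.

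**What to change.** 1. **SAP 4.5.2 and 4.8.** Keep the 4-week treatment-emergent window for the tables. State one anchor date, the last dose, in place of the present two alternatives. Enter the narrowing of Protocol 9.3.5 in SAP 4.8 with its reason.
2. **SAP listings.** Add one listing of all AEs and SAEs with onset after the window in participants still in the study. State in 4.5.2.1 that the AESI listing has no treatment-emergent limit.
3. **Protocol 8.4.1.** Reconcile the AE and SAE sentences with each other, with Section 8.3 and with SoA notes t and n, so that one eCRF recording end point applies: the participant's last study visit.
4. **Protocol 7.1 and the SoA early-termination footnote.** Reconcile them so that sites know which visits apply to a participant who stops drug but stays in the study.

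The cost is wording in both documents, one extra listing and a few later AE entries. The visits and AE questions are already scheduled. Some added entries will be off-drug events; the separate listing keeps them out of the treatment-emergent percentages, which do not change.

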- The proportions of participants who experienced 1 or more AEs were similar in the combined JNJ-77242113 (52.4%) and placebo (51.2%) groups.
- The most frequently reported AEs were in the Infections and infestations system organ class (SOC) and were similar between the combined JNJ-77242113 (30.2%) and placebo (27.9%) groups. The most common AEs by preferred term (PT) in this SOC were COVID-19 (10.8% and 11.6%), nasopharyngitis (7.1% and 4.7%), and upper respiratory tract infection (2.4% and 2.3%) in the combined JNJ-77242113 and placebo groups, respectively. In the Gastrointestinal disorders SOC, AEs were reported in 11.3% of participants in the combined JNJ-77242113 group and 11.6% in the placebo group. Other AEs by PT reported by at least 5% of participants included headache and cough.
- The percentage of participants with 1 or more serious adverse events (SAEs) through the end of study was small, with 3 participants (1.4%) experiencing 1 SAE each. All events were singular in nature and deemed not related to study intervention per the investigator.
- The proportion of participants who discontinued study intervention due to 1 or more AEs was small (n=6). Three out of the 6 events were in the Gastrointestinal SOC (n=1 each: abdominal pain, abdominal discomfort, and nausea). The other 3 events included suicide attempt, weight increase, and transaminases increase (n=1 each).
- Rates of abnormal laboratory test result were generally low and comparable between the treatment groups.
- There were no deaths or malignancies reported.

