### Adverse Events

The verbatim terms used in the CRF by investigators to identify AEs will be coded using the Medical Dictionary for Regulatory Activities (MedDRA). Any AE occurring at or after the initial administration of study intervention or that is a consequence of a pre-existing condition that has worsened since baseline is considered to be treatment-emergent. All reported treatment-emergent AEs will be included in the analysis. For each AE, the percentage of participants who experience at least 1 occurrence of the given event will be summarized.

The following analyses will also be used to assess the safety of participants in the study:

- The incidence and type of AEs.
- The incidence and type of SAEs.
- The incidence and type of AESIs.
- The incidence and type of severe AEs.
- The incidence and type of treatment-related AEs and SAEs as assessed by the investigator.
- The incidence and type of AEs leading to discontinuation of study intervention.

Listings of participants with SAEs, severe AEs, AEs of psoriasis, AESIs, and AEs leading to discontinuation of study intervention will also be provided. Summaries, listings, datasets, or participant narratives may be provided, as appropriate, for those participants who die, who discontinue intervention due to an AE, or who experience a severe or an SAE.

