1.2. Study Design

This is a Phase 3, open-label, multicenter study to evaluate the efficacy and safety of JNJ-77242113 for the treatment of participants with generalized pustular psoriasis (GPP) or erythrodermic psoriasis (EP).

A target of 16 (GPP, n=8; EP, n=8) participants will be enrolled in this study. All participants will take JNJ-77242113 from Week 0.

The total duration of this study for each participant is approximately 165 weeks, which includes: a ~5-week screening period, a 52-week treatment period, a 104-week long term extension treatment period (LTE), and a 4-week safety follow-up period.

All the participants will receive JNJ-77242113 200 mg once daily for 52 weeks. Participants completing Week 52 visit may be eligible to enroll in the LTE. The LTE will begin at the end of Week 52 and will continue until Week 156. All the participants will have a 4-week safety follow up period at the end of the treatment period or after the last dose of study intervention.

Efficacy, safety, PK, immunogenicity, and biomarkers will be assessed according to the Schedule of Activities in protocol Section 1.3. In addition, there will be 2 optional substudies for participants who provide consent. Sample collections for these substudies include a pharmacogenomic blood sample and photograph collection.

The first database lock (DBL) will occur when all participants complete Week 24 of the study. Additional DBLs may occur after Week 24 to support regulatory submissions and scientific disclosures.

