4.5. Safety Analyses

The safety data will be summarized based on SAS and it will be presented by diagnosed disease (GPP or EP), and 'GPP+EP' column that combines GPP and EP will also be presented.

For all continuous safety variables, descriptive statistics will include the N, mean, standard deviation, median, minimum, and maximum. Categorical variables will be summarized by using frequency counts and percentages.

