4.5.1. Extent of Exposure

For the following parameters, descriptive statistics will be presented of continuous variables and categorial variables frequency counts and percentages will be presented.

- Treatment duration (weeks)
 - (date of last dose of study intervention – date of first dose of study intervention + 1 day) /7.
- Average daily dose
 - (tablets dispensed – tables retuned) x tablet strength /(date of last dose of study intervention – date of first dose of study intervention + 1 day).

Study intervention compliance will also be summarized descriptively. See [Appendix 7](#) for further details.

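### The AE and SAE summary tables give crude percentages with no exposure adjustment and no common cut-off at the first lock, so the figures rise with follow-up and cannot be compared across locks or with Phase 2b

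*SAP*

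**What the plan says.** The summary measure for treatment-emergent events in SAP 4.5.2 is: "For each adverse event, the number and percentage of participants who experience at least 1 occurrence of the given event will be summarized". Protocol 9.3.5 plans the same: "For each AE, the percentage of participants who experience at least 1 occurrence of the given event will be summarized". Frequency and type of AEs and SAEs is a listed secondary endpoint in both documents.

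Four features decide how much observation time lies behind each percentage:

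- **Window.** Under SAP 4.5.2 an event from first dose "up to 4 weeks after the last dose or treatment discontinuation is considered to be treatment emergent", so the window lengthens with each participant's treatment.
- **First lock.** SAP 1.2 states: "The first database lock (DBL) will occur when all participants complete Week 24 of the study". It does not say that each participant's data are cut at that participant's own Week 24.
- **Later locks.** SAP 1.2 allows further locks but does not fix their timing. Protocol 4.1 leaves lock details to the SAP as necessary, and the SAP only repeats the protocol's statement.
- **Extension.** Participants who complete Week 52 may enter the LTE, so planned treatment is 52 or 156 weeks.

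The SAP also lists a table called "AEs by study period", whose periods it does not define, as well as a summary of treatment duration (4.5.1) and listings of AEs and SAEs. For all safety output, "it will be presented by diagnosed disease (GPP or EP), and 'GPP+EP' column that combines GPP and EP will also be presented".

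**The concern.** The percentage of participants with at least one event is a cumulative quantity: it can only rise as observation lengthens. It describes risk well when everyone is observed for the same known time. Here earlier enrolees can contribute more than 24 weeks to the first lock, later locks have no set date, and only those who enter the LTE contribute beyond Week 52.

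Three comparisons that readers of the study report are likely to make are then unsafe: one lock against another, participants with LTE follow-up against those without, and this study against the 16-week Phase 2b safety figures in Protocol 2.2. A later table could look worse than an earlier one with no change in risk. By the end of the extension the any-AE percentage may be so close to 100% that it says little.

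**Working it through.** **The plan's own figure.** Planned duration per participant is 5 + 52 + 104 + 4 = 165 weeks, which matches the stated total. The sample of 8 + 8 = 16 is set by feasibility, so there is no power formula to reproduce.

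**Inputs.** Protocol 2.2 gives the Phase 2b safety results. The bullet beginning "The proportions of participants who experienced 1 or more AEs were similar in the combined" reports 52.4% on active drug, and another reports 3 participants (1.4%) with an SAE. Study length was 16 weeks. The SAE figure runs to the end of that study, so 20 weeks was also tried. Using plaque-psoriasis risks for GPP and EP, and holding the hazard constant, are assumptions made for illustration.

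**Formula.** Weekly hazard λ = −ln(1 − p)/16. Crude percentage at week t = 1 − exp(−λt).

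- Any AE: λ = −ln(0.476)/16 = 0.0464 per week.
- SAE: λ = −ln(0.986)/16 = 0.00088 per week.

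| Weeks observed | Any AE | SAE |
|---|---|---|
| 16 | 52.4% | 1.4% |
| 24 | 67.2% | 2.1% |
| 52 | 91.0% | 4.5% |
| 156 | 99.9% | 12.8% |

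With a 20-week SAE window the Week 156 figure is 10.4%.

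**With and without the LTE.** The event window is 52 + 4 = 56 weeks for a participant who stops at Week 52 and 156 + 4 = 160 weeks for one who completes the LTE. Any AE is 92.6% against 99.9%, and SAE is 4.8% against 13.2%.

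**First lock.** The accrual span is not given, so 0 to 78 weeks was tried, with follow-up uniform between 24 weeks and 24 weeks plus the span. In simulation, the expected any-AE percentage at spans of 0, 12, 26, 52 and 78 weeks is 67.2%, 74.8%, 80.9%, 87.6% and 91.2%. Without a cut-off, the speed of enrolment alone moves the first reported figure.

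**GPP against EP.** In the same simulation with 8 per group, chance differences in follow-up explain 0%, 0.9%, 2.8%, 6.3% and 8.8% of the variance of the any-AE difference at those spans, and under 1% for SAEs. A systematic gap of 28 against 48 weeks (also an assumption) gives 72.7% against 89.2%. That difference of 16.5 points has a standard error of √(0.727×0.273/8 + 0.892×0.108/8) = 19.2 points. For SAEs the shift is 1.7 points against a standard error of 8.9.

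**What a rate would show.** Under the same assumptions the first-event rates are 0.0464 × 52.18 × 100 ≈ 242 for any AE and about 4.6 for SAEs, per 100 participant-years at risk. Under a constant hazard these do not change with the lock date.

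**Whether existing output covers it.** Because its periods are undefined, the table by study period cannot be relied on to give a common window. Treatment duration runs from first to last dose and leaves out the 4-week tail in which events still count, so it is not the matching denominator.

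**The case against.** The case for leaving the plan alone is reasonable. The study is single-arm and descriptive, with 16 participants and no formal hypothesis testing. No comparison of GPP with EP, or with Phase 2b, is planned. Counts and percentages do deliver an endpoint worded as frequency and type. They are not the only AE output: there are listings, a duration summary and a table by period, and a reader could work out rates for 16 people by hand. On the natural reading that the periods are the 52-week treatment period and the LTE, the first-period column would have a common planned window once everyone has passed Week 52. The growth figures borrow a constant hazard from another population. If participants differ in susceptibility, 99.9% at Week 156 is too high.

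Much of this stands, and it keeps the point minor. It does not remove it. The natural reading of the periods is not written down and would not equalise follow-up at the first lock. Rates worked out by hand are not a prespecified summary. The borrowed hazard affects the size of the growth, not its direction. The SAP itself recognises in 4.6.2.2 that cumulative antibody status changes between locks, but gives no equivalent guidance for AEs.

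**Conclusion.** The point holds for comparisons across locks, between participants with and without LTE follow-up, and with the 16-week Phase 2b results. Under the constant Phase 2b hazard, an unchanged risk appears as 67.2%, 91.0% and 99.9% with any AE at Weeks 24, 52 and 156. The SAE percentage goes from 1.4% at 16 weeks to 12.8% at Week 156, about ninefold (10.4% if the Phase 2b SAE window was 20 weeks).

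A reader might infer more: that follow-up differs between GPP and EP at every lock, and that the percentages mainly reflect follow-up time. The documents do not support this. Both diseases share one schedule, and no accrual or dropout figures are given by disease. A gap is possible, but at 8 per group chance follow-up differences explain at most about 9% of the variance of the contrast over the spans tried. At a final lock staggered entry no longer matters, and only discontinuation and non-entry to the LTE leave follow-up unequal.

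Severity is minor. The change is worth making because it is cheap and concerns a stated secondary endpoint.

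**What to change.** In SAP 4.5.2, keep the crude tables and make three changes:

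1. For the first lock, add an AE and SAE table cut at each participant's Week 24.
2. Define the periods in the table by study period, for example Week 0 to 52 and LTE.
3. For AEs, SAEs and AEs leading to discontinuation, add participant-years of follow-up and events per 100 participant-years with an exact Poisson 95% CI. Follow-up runs from first dose to the earlier of last dose + 4 weeks or the data cut-off. The cut-off should be stated for each lock.

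The cost is SAP wording and a few extra columns, using dates already collected. Intervals will be wide. With 0 events in 8 participants over 24 weeks there are 8 × 24/52.18 = 3.68 participant-years, and the upper limit is −ln(0.025)/3.68 = 3.69/3.68, or about 100 per 100 participant-years. The crude percentage is also imprecise: 0 of 8 has an exact upper limit of 36.9%, and 5 of 8 has an interval of 24.5% to 91.5%. Where one participant has repeated events, the Poisson interval treats them as independent, and a footnote should say so.
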